4.5.7.3 Bleed and Medication Questionnaire

Patients (or their legally authorized representative) will complete a BMQ whenever a bleed occurs or at least on a weekly basis (retrospective reporting for last 7 days) via an electronic, handheld device. For each bleed episode, the patient will provide information regarding bleed start date and time, reason, type, location, and associated symptoms (only collected for muscle and joint bleeds in patients 12 years of age and older). Hemophilia medications and reason for treatment (e.g., bleed, surgery, physical activity) will also be collected through the use of the BMQ. If the electronic, handheld device is not available, a paper questionnaire might be used. Investigators will review the bleed and bleed medication data as per the schedule of activities (see Appendix 1) and will have the option to correct or complete the BMQ in agreement with the patient via a Data Request Form process or via a web-based portal, once implemented. The Sponsor will have view-access only but will perform a review of the bleed and bleed medication data as per the Medical Data Review Plan.

4.5.7.4 Bleed Definitions and Reporting Definition of a Bleed

For the purpose of the efficacy analyses, a standardized definition of bleed, adapted from criteria defined by the Subcommittee on Standards and Criteria, FVIII/Factor IX subcommittee of the International Society of Thrombosis and Hemostasis, and similar to that used in a recent clinical study, will be used in this study (Blanchette et al. 2014; Mahlangu et al. 2014) as follows:

- An event is considered a treated bleed if coagulation factors are administered to treat signs or symptoms of bleeding (e.g., pain, swelling). An additional definition of all reported bleeds (irrespective of treatment with coagulation factors) will be applied for a separate analysis.
- Bleeds starting from the first sign of bleed and ending 72 hours after the last treatment for the bleed, within which any symptoms of bleeding at the same location or injections are ≤72 hours apart, are considered the same bleed.
- Any injection to treat the bleed, taken > 72 hours after the preceding injection, is considered the first injection to treat a new bleed at the same location.
- Any bleed at a different location is considered a separate bleed regardless of time from last injection.

Definition of Bleed Sites

Bleed sites are defined as follows:

Target joints: defined as a major joint (e.g., hip, elbow, wrist, shoulder, knee, and ankle) into which repeated bleeds occur (frequency of ≥ 3 bleeds into the same joint over the last 24 weeks prior to study entry) or as an unresolved target joint. An unresolved target joint is defined as a target joint that does not fulfil the criterion of ≤ 2 bleeds into this joint within a consecutive 12-month period (Blanchette et al. 2014).

Emicizumab—F. Hoffmann-La Roche Ltd 51/Protocol BO41423, Version 3

- Joint bleeds: defined as bleeds with bleed type "joint bleed" reported via the BMQ with at least one of the following symptoms:
 - Increasing swelling or warmth of the skin over the joint
 - Increasing pain
 - Progressive loss of range of motion or difficulty in using the limb as compared with baseline
- Muscle bleeds (sites as per the BMQ)
- Other (sites as per the BMQ)

Definitions of Bleed Types

The assessment of a bleed will be separated into spontaneous bleeds, traumatic bleeds, and bleeds related to procedure/surgery. Both spontaneous bleeds (i.e., the occurrence of hemorrhage where neither the patient nor a caregiver can identify a reason) and traumatic bleeds (i.e., hemorrhage occurring secondary to an event such as trauma, "strenuous" activity, or "overuse") will be collected.

- Spontaneous bleeds: Bleeds should be classified as spontaneous if a patient records a bleed when there is no known contributing factor such as definite trauma, antecedent "strenuous" activity, or "overuse." The determination of what constitutes "strenuous" or "overuse" will be at the discretion of the patient. For example, light jogging may be considered "non-strenuous," while sprinting may be considered "strenuous," lifting of weights for a short period of time may be considered "moderate use," while repetitive weightlifting may be considered "overuse."
- Traumatic bleeds: Bleeds should be classified as traumatic if a patient records a bleed when there is a known or believed reason for the bleed. For example, if a patient were to exercise "strenuously" and then have a bleed in the absence of any obvious injury, the bleed would be recorded as a traumatic bleed because, although no injury occurred, there was antecedent "strenuous" activity. Bleeds subsequent to injuries would certainly be classified as traumatic.
- Bleeds related to procedure/surgery: For example, hematomas resulting from any surgery or invasive procedure (e.g., tooth extractions, venipuncture, or SC drug administrations), or invasive diagnostic procedures (e.g., lumbar puncture, arterial blood gas determination, or any endoscopy with biopsy) would not be considered a bleed related to procedure/surgery. Such bleeds are not associated with any trauma except procedure/surgery-induced trauma.

Reporting of Bleed Data

Patients will complete a BMQ weekly and whenever a bleed occurs via an electronic, handheld device. For each bleeding episode, the patient will provide information on the above topics as well as on the medication used to treat the bleed. Hemophilia medications that were taken will also be collected through the BMQ. If the electronic, handheld device is not available, a paper questionnaire might be used. Investigators will review the bleed and bleed medication data as per the schedule of assessments

Emicizumab—F. Hoffmann-La Roche Ltd 52/Protocol BO41423, Version 3

(see Appendix 1) and have the option to correct or complete these in agreement with the patient via a Data Request Form process or via a web-based portal, once implemented.

The Sponsor will have view-access only but will perform a review of the bleed and bleed medication data as per the Medical Data Review Plan and have the option to correct or complete these in agreement with the patient via a Data Request Form process or via a web-based portal, once implemented.

Reporting of Menstrual Bleed and Menstruation Diary Data

All female patients of childbearing potential will be asked to complete the following paper questionnaire and diary:

- MBQ in the clinic on Day 1 and subsequently every 4 weeks to document the menstrual bleed-related heaviness, pain, irregularity, and quality of life during the past month (See Appendix 13).
- MD with the PBAC to document at home the use of menstrual products during the
 past month (including the number of products used, the amount of bleeding, the
 occurrence and size of clots, and the number of episodes of heavy bleeding
 (flooding)). The MD with PBAC will be given to patients on Day 1 and should be
 completed monthly on days of menstruation (See Appendix 14). The patient should
 return the completed MD with PBAC to the site personnel during the next clinic visit.

All MBQ and MD data will be entered into the study database by site personnel.

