2.2 EFFICACY OBJECTIVES

2.2.1 Primary Efficacy Objective

The primary efficacy objective for this study is to evaluate the efficacy of emicizumab on the basis of the following endpoint:

• Number of treated bleeds over time (i.e., bleed rate)

2.2.2 Secondary Efficacy Objectives

The secondary efficacy objective for this study is to evaluate the efficacy of emicizumab on the basis of the following endpoints:

- Number of all bleeds (i.e., those treated and untreated with FVIII) over time
- Number of joint bleeds over time
- Number of target joint bleeds over time (target joints are defined as joints with ≥3 bleeds occurring in the same joint during the last 24 weeks or unresolved target joints)

An unresolved target joint is defined as a target joint that does not fulfil the criterion of ≤ 2 bleeds into this joint within a consecutive 12-month period.

- Number of spontaneous bleeds over time (spontaneous bleed rate)
- Joint health, as assessed through use of the Hemophilia Joint Health Score (HJHS) at specified timepoints
- Health-related quality of life (HRQoL), as assessed through use of the Comprehensive Assessment Tool of Challenges in Hemophilia (CATCH) Questionnaire over time
- Preference for emicizumab compared with previous FVIII regimen, as assessed through use of the Emicizumab Preference Survey (EmiPref) at Week 17
- Effect of emicizumab prophylaxis treatment on physical activity compared with physical activity at baseline
- Effect of emicizumab prophylaxis treatment on menstruation heaviness and menstruation-related quality of life in female patients of childbearing potential, as assessed through the use of the Menstrual Bleeding Questionnaire (MBQ) and the Menstruation Diary (MD) with the Pictorial Blood Assessment Chart (PBAC) over time

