6.5.2.1 Bleed Endpoints

The clinical effect of prophylactic emicizumab on the secondary bleed endpoints of all bleeds (i.e., those treated and untreated with coagulation factors), joint bleeds, target joint bleeds, and spontaneous bleeds (see Section 4.5.7.3 for bleed definitions) will be analyzed in the same manner as for the primary analysis.

The number of bleeds, sites of bleeds, and types of bleeds will be summarized for all patients and listed for each patient individually. Several exploratory analyses will be conducted to characterize the type, location, duration, frequency, and pattern of bleeds. For continuous endpoints, descriptive statistics will be calculated and categorical endpoints will be characterized through frequency tables.

6.5.2.2 Health-Related Quality-of-Life, Patient Preference, Joint Health, Activity, Menstruation Heaviness, and Menstruation-Related Quality of Life

With regards to the PRO secondary objectives, scores by each domain for the CATCH will be computed for each assessment with changes in scores examined for the assessments over time, and these will be summarized descriptively. Patient compliance with the CATCH will be summarized at each assessed timepoint.

For the EmiPref, the proportion of patients/caregivers preferring emicizumab after 17 weeks of treatment will be presented along with the reasons for that choice. Patient/caregivers compliance with the EmiPref will be summarized for Week 17.

For the activity assessment and HJHS, descriptive analyses will be presented by timepoints. All enrolled subjects who contribute to valid activity data (e.g., at least 8 days of wearing the device within a 14-day observation period) will be analyzed for

Emicizumab—F. Hoffmann-La Roche Ltd 79/Protocol BO41423, Version 3

activity. The definition of valid activity data and the handling of missing values will be provided in the SAP.

Relative change from baseline (Weeks 1–2 period) at Weeks 13 (Weeks 12–13 period), 25 (Weeks 24–25 period), 37 (Weeks 36–37 period), and 49 (Weeks 48–49 period) in mean MVPA and DSC will be calculated and summarized. Subject-level data will also be presented at each timepoint.

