3.1 ANALYSIS POPULATIONS

3.1.1 All Patients Population

The All patients population includes all patients enrolled in the trial. This population will be used to describe demographic and baseline characteristics.

3.1.2 Treated Population

The Treated population corresponds to all patients who received at least one dose of emicizumab. This population will be the primary population for efficacy and safety analyses.

Emicizumab —F. Hoffmann-La Roche Ltd 9/Statistical Analysis Plan BO41423

3.1.3 Pharmacokinetic-Evaluable Population

The PK-Evaluable population includes all patients who have received at least one dose of emicizumab and have at least one post-baseline emicizumab plasma concentration result.

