3.3.2.1 Bleed Rate

The efficacy of emicizumab is characterized by the number of bleeds over time. This will be calculated using a negative binomial (NB) regression model, which accounts for different follow-up times, with time that each patient stays in the study (efficacy period) included as an offset in the model. In addition, the number of bleeds will also be annualized for each patient using the following formula:

Annualized bleed rate (ABR) = (Number of bleeds/number of days during the efficacy period) \times 365.25.

The mean and median ABR based on the above formula using the observed numbers of bleeds instead of the number resulting from the model will also be calculated. In the case where the negative binomial model does not converge, the alternative derivations of the ABR will be used as the sole method of analysis.

ABR corresponding to treated bleeds, all bleeds, treated joint bleeds, treated target joint bleeds, and treated spontaneous bleeds will be analyzed in a similar manner. These will be summarized for all patients and listed for each patient individually. Several exploratory analyses will be conducted to characterize the type, location, and frequency.

3.3.2.1.1 72-Hour Rule:

Two bleeds of the same type (e.g., "joint", "muscle", or "other") and at the same anatomical location are considered to be one bleed if the second bleed occurs within 72 hours from the last treatment for the first bleed. The last treatment is defined as the last treatment before a new bleed occurs, either in the same or in a different location.

Bleeding rates and characteristics of bleeding describing location and type will also be provided using the 72-hour rule.

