3.3.3 Subgroup Analyses

Additional descriptive summaries of both treated bleeds and all bleeds will be computed for various subgroups of the study. The summaries will include subgroup ABR and its 95% CIs. The main pre-specified subgroups are as follows:

- Age: 0 to <2, 2 to <6, 6 to <12, 12 to <18, 18 to <65, ≥65 years
- Race: Asian, Black or African American, White, Other
- Hemophilia severity: mild, moderate
- Number of target joints at study entry: no target joint, any target joint
- Previous treatment regimen: prior episodic, prior prophylactic
- Prior FVIII inhibitor: Yes/No
- Female patient: Yes/No
- Dosing regimens at enrolment: 1.5 mg/kg QW, 3 mg/kg Q2W, 6 mg/kg Q4W

Note that due to the likely small sample sizes, subgroup analyses will be highly susceptible to variability and should therefore be interpreted with caution.

Emicizumab —F. Hoffmann-La Roche Ltd 12/Statistical Analysis Plan BO41423 Additional region- and/or country-specific analyses may be performed to support regulatory submissions as needed.

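### Joint bleeds need a symptom the BMQ does not collect under age 12, so as written the pooled joint-bleed ABR counts children's time but none of their joint bleeds

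*Protocol*

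**What the plan says.** **Definition.** Protocol 4.5.7.4 is the only place in either document that defines a joint bleed. The event must be of BMQ type joint bleed, "reported via the BMQ with at least one of the following symptoms": swelling or warmth, pain, or reduced movement or use of the limb. There is no exception by age. Muscle and other bleeds need only a BMQ site.

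**Data collected.** Protocol 4.5.7.3 describes the symptom item as "associated symptoms (only collected for muscle and joint bleeds in patients 12 years of age and older". The same restriction stands in the BMQ footnote of protocol Appendix 1, in SAP 2.2.1 and in the BMQ footnote of SAP Appendix 2.

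**Analysis.** Protocol 6.5.2.1 analyses "joint bleeds, target joint bleeds, and spontaneous bleeds (see Section 4.5.7.3 for bleed definitions" in the same way as the primary endpoint. The SAP uses the Treated population (3.1.2): "This population will be the primary population for efficacy and safety analyses". The model in SAP 3.3.2.1 is negative binomial, "with time that each patient stays in the study (efficacy period) included as an offset in the model". It adds that "treated joint bleeds, treated target joint bleeds, and treated spontaneous bleeds will be analyzed in a similar manner".

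**Ages.** Protocol 3.1 enrols all age groups, and SAP 3.3.3 pre-specifies three age strata below 12. Those subgroup tables do not cover joint bleeds: "Additional descriptive summaries of both treated bleeds and all bleeds will be computed for various subgroups of the study".

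**The concern.** The definition depends on an item that is never asked of patients under 12. Read literally, these children contribute follow-up time to the joint-bleed rate but can contribute no events. A target-joint bleed is affected in the same way if it must first qualify as a joint bleed, which the documents do not say.

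The error runs in the drug's favour on joint protection. It would also be hard to notice in the summary tables, because no planned table shows joint-bleed ABR by age. If a programmer avoids the problem by using bleed type alone, the analysis departs from the only written definition. Two analysts could then report different joint-bleed ABRs from the same data.

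Two smaller mismatches affect the same endpoints:

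- The protocol does not say whether joint, target-joint and spontaneous bleeds are limited to treated ones; SAP 3.3.2.1 analyses treated ones only.
- Protocol 2.2.2 counts as target joints those with three or more "bleeds occurring in the same joint during the last 24 weeks or unresolved target joints". SAP 2.3.2 lacks the unresolved limb, and the SAP's appended synopsis is that of protocol Version 2.

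**Working it through.** The documents give no joint-bleed rate and no expected number of children, so there is no stated figure to reproduce. The check has three parts.

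**1. Is there a rule that rescues the under-12s?** SAP 3.8 deals only with missing times of bleeds and treatments. It also says the handheld device does not allow unanswered questions, so an absent symptom in a child is a question not asked rather than a missing value. Protocol 4.5.7.3 lets investigators correct or complete the BMQ, but nothing provides for collecting symptoms under 12. No rule was found.

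**2. Size of the bias.** Let L be the joint-bleed rate at 12 and over, s the under-12 share of person-time, and r the under-12 rate divided by L. Both s and r are assumptions.

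- Rate with all joint bleeds counted: L(1 − s + s·r)
- Rate under the written rule: L(1 − s)
- Understatement: s·r / (1 − s + s·r)

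Example: with s = 0.2 and r = 1, the understatement is 0.2 / (0.8 + 0.2) = 20%. With s = 0.4 and r = 2, it is 0.8 / (0.6 + 0.8) = 57%.

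| s | r = 0.5 | r = 1 | r = 2 |
|---|---|---|---|
| 0.1 | 5% | 10% | 18% |
| 0.2 | 11% | 20% | 33% |
| 0.3 | 18% | 30% | 46% |
| 0.4 | 25% | 40% | 57% |

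**3. Does the planned model behave the same way?** An intercept-only negative binomial model with a log-time offset was fitted to simulated trials. Assumptions: 70 patients, 0.8 to 1.3 years each, true joint-bleed rate 1.0 per year at all ages (r = 1), dispersion 2, 800 trials per scenario. Mean estimated ABR:

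| Under-12s of 70 | All joint bleeds counted | As written | Ratio | Patients 12 and over only |
|---|---|---|---|---|
| 7 (10%) | 1.00 | 0.90 | 0.90 | 1.00 |
| 14 (20%) | 1.02 | 0.81 | 0.79 | 1.01 |
| 21 (30%) | 1.00 | 0.70 | 0.70 | 1.00 |
| 28 (40%) | 1.01 | 0.61 | 0.61 | 1.02 |

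The model reproduces the algebra. A second set of simulations (600 trials per scenario, follow-up 0.8 to 1.4 years) gave as-written means of 0.89, 0.81 and 0.61 with 7, 14 and 28 children. The forced zeros also raised the median estimated dispersion from about 1.9 to 2.3, 2.8 and 4.1.

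**The case against.** The strongest reply is that nobody will apply a symptom filter to children. The 72-hour rule in SAP 3.3.2.1 groups events by type (joint, muscle, other) and location, and no SAP analysis section mentions symptoms. If joint bleeds are taken by type alone, there is no downward bias. That is true, but the 72-hour rule merges events and does not say what a joint bleed is. The bias is therefore conditional on applying the text as written; the alternative abandons that text without saying so.

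Protocol 6.5.2.1 points to Section 4.5.7.3 for definitions, and that section sets no symptom requirement. This looks like a cross-reference slip: the definitions are in the adjacent 4.5.7.4.

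Several limits do stand. The size is unknown, because s and r are assumed and the simulation confirms the algebra without saying anything about this trial's enrolment. The endpoint is secondary in a study with no hypothesis tests. Bleeds are also to be listed patient by patient, so a careful reader could find a child's joint-type bleed missing from the joint count.

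On the smaller points, the treated-only wording can be read as the SAP specifying what the protocol left open, and the target-joint difference as version lag. Both are housekeeping, and the main point does not depend on them.

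**Conclusion.** The concern holds. The written definition and the data collection plan are incompatible for patients under 12, and with their time left in the offset the pooled joint-bleed ABR is too low. The direction is certain once one treated child under 12 has a joint bleed and the definition is applied as written. The magnitude cannot be fixed from the documents; the tabulated 5% to 57% covers assumed under-12 shares of 10% to 40% and rate ratios of 0.5 to 2.

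The primary treated-bleed ABR, the all-bleeds ABR and the planned age-subgroup tables are not affected. This should be fixed before the analysis, but it does not threaten the main result.

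**What to change.** - In protocol 4.5.7.4 and SAP 3.3.2.1, define a joint bleed under age 12 by BMQ type and location without the symptom criterion. State whether age is taken at enrolment or at the bleed, since some children will turn 12 on study.
- Alternatively, exclude under-12s from both the count and the offset for the joint endpoints. This also removes the bias, but it narrows the endpoint population in an all-ages trial.
- State whether a target-joint bleed must first meet the joint-bleed definition, and correct the section reference in protocol 6.5.2.1.
- Add a table of joint-bleed ABR below 12 and at 12 and over.
- State in both documents whether the joint, target-joint and spontaneous endpoints are treated-only.
- Bring SAP 2.3.2 into line with the Version 3 target-joint definition, and check that the pre-study bleed history required (at least 24 weeks, protocol 4.1.1) can support its 12-month criterion.

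The cost is wording in two documents and one programming branch by age. Type and location are already collected at all ages, so no new data item is needed. The downside of the first option is some loss of specificity for joint bleeds in children; the documents give no figure for it.

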4.1.2 Exclusion Criteria

Patients who meet any of the following criteria will be excluded from study entry:

- Inherited or acquired bleeding disorder other than mild (FVIII level between > 5% and <40%) or moderate (FVIII level between ≥1% and ≤5%) congenital hemophilia A
- History of illicit drug or alcohol abuse within 48 weeks prior to screening, in the investigator's judgment

Emicizumab—F. Hoffmann-La Roche Ltd 36/Protocol BO41423, Version 3

- Previous (within the last 12 months) or current treatment for thromboembolic disease (with the exception of previous catheter-associated thrombosis for which anti-thrombotic treatment is not currently ongoing) or signs of thromboembolic disease
- Other conditions (e.g., certain autoimmune diseases) that may currently increase the risk of bleeding or thrombosis
- History of clinically significant hypersensitivity associated with monoclonal antibody therapies or components of the emicizumab injection
- Planned surgery during the emicizumab loading dose phase
 Surgeries in patients on emicizumab from Week 5 onwards are allowed.
- Known HIV infection with CD4 counts < 200 cells/μL
- Concomitant disease, condition, significant abnormality on screening evaluation or laboratory tests, or treatment that could interfere with the conduct of the study, or that would in the opinion of the investigator, pose an additional unacceptable risk in administering study drug to the patient
- Receipt of any of the following:
 - An investigational drug to treat or reduce the risk of hemophilic bleeds within 5 half-lives of last drug administration with the exception of prior emicizumab prophylaxis (prior investigational or commercial emicizumab use is not an exclusion criterion)
 - A non-hemophilia-related investigational drug within last 30 days or 5 half-lives, whichever is shorter
 - Any other investigational drug currently being administered or planned to be administered
- Inability to comply with the study protocol in the opinion of the investigator
- Pregnant or breastfeeding, or intending to become pregnant during the study
 Women of childbearing potential must have a negative serum pregnancy test result within 7 days prior to initiation of study drug.

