5.1.1 Risks Associated with Emicizumab

5.1.1.1 Injection-Site Reactions

Injection-site reactions have been observed in patients with hemophilia A. These local injection-site reactions included erythema, hematoma, rash, discomfort, pain, and pruritus and were mostly of mild and moderate intensity. Further details for observed injection-site reactions are available in the RO5543262 (Emicizumab) Investigator's Brochure. Directions for emicizumab administration should be followed, as outlined in Section 3.3.1 and Section 4.3.2.

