5.3.5.1 Injection-Site Reactions

Local adverse events that occur within 24 hours after study drug administration and are judged to be related to study drug injection should be captured as an "injection-site reaction" on the Adverse Event eCRF. If possible, avoid ambiguous terms such as "systemic reaction." Associated signs and symptoms (e.g., injection-site erythema or injection-site rash) should be recorded on the dedicated Injection-Site Reaction eCRF. If a patient experiences both a local and systemic reaction to the same administration of study drug, each reaction should be recorded separately on the Adverse Event eCRF. Only for local injection-site reactions should the dedicated Injection-Site Reaction eCRF be used to capture the individual signs/symptoms.

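### The procedure/surgery bleed class in Protocol 4.5.7.4 excludes its own six examples, so bleeds summarized by cause would be misclassified if the rule is applied literally

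*Protocol*

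**What the plan says.** Protocol 4.5.7.4, under Definitions of Bleed Types, sets up three cause classes: "The assessment of a bleed will be separated into spontaneous bleeds, traumatic bleeds, and bleeds related to procedure/surgery". Spontaneous requires that no contributing factor is known. For the second class, "Bleeds should be classified as traumatic if a patient records a bleed when there is a known or believed reason for the bleed". The third bullet, on procedure/surgery, names six sources of hematoma: tooth extraction, venipuncture, subcutaneous drug injection, lumbar puncture, arterial blood gas sampling and endoscopic biopsy. It says that these "would not be considered a bleed related to procedure/surgery. Such bleeds are not associated with any trauma except procedure/surgery-induced trauma".

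The counting rules are in the same section and make no reference to cause. "An event is considered a treated bleed if coagulation factors are administered to treat signs or symptoms of bleeding (e.g., pain, swelling"). All bleeds means every reported bleed, whether or not factor was given. SAP 3.3.2.1 plans five ABRs: treated, all, treated joint, treated target joint and treated spontaneous.

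On output, Protocol 6.5.2.1 states: "The number of bleeds, sites of bleeds, and types of bleeds will be summarized for all patients and listed for each patient individually". SAP 3.3.2.1 adds exploratory characterization of type, location and frequency. SAP 3.3.2.1.1 illustrates type as joint, muscle or other.

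The 72-hour rule is worded two ways. Protocol 4.5.7.4 refers to both *injection* and *treatment*, while SAP 3.3.2.1.1 refers only to *treatment*. Neither says which drug classes count, although Protocol 4.4.1 permits bleed-control drugs other than FVIII.

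**The concern.** Both halves of the procedure/surgery bullet cannot stand. The heading and the second sentence say that the class holds bleeds whose only trauma is the procedure. The first sentence takes exactly those bleeds out. Patients enter the reason for a bleed in the Bleed and Medication Questionnaire (BMQ), and investigators may correct it. This section is the only text that they can consult, so the contradiction sits in an operative definition.

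Procedural bleeds can be expected. The protocol says "Surgeries in patients on emicizumab from Week 5 onwards are allowed", every patient receives subcutaneous injections, and Appendix 2 schedules blood sampling at 16 visits from Week 1 to Week 49.

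There are two ways to follow the sentence. One moves the bleed to traumatic. The other treats the hematoma as no bleed at all. A site has some reason to take the second route for injection hematomas. Among the known reactions to emicizumab, "These local injection-site reactions included erythema, hematoma, rash, discomfort, pain, and pruritus" are listed, and Protocol 5.3.5.1 sends "Local adverse events that occur within 24 hours after study drug administration and are judged to be related to study drug injection" to the Adverse Event eCRF as injection-site reactions. In a single-arm descriptive study the bleed counts and their description are the result, so the sponsor should say which reading it means.

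**Working it through.** No alpha, power or sample-size figure depends on this text, so there is no stated figure to reproduce. The check is logical, with one illustration.

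**Step 1: the class.** Six examples are named in the bullet and the *not* governs all of them, so 6 of 6 leave the class. Each has a known reason, so each meets the traumatic definition and fails the spontaneous one.

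**Step 2: the five ABRs under the relabelling reading.** Treated and all bleeds do not depend on cause. Treated joint and treated target joint depend on site. Treated spontaneous depends on cause, but a bleed moved from procedural to traumatic was never spontaneous. ABRs changed: 0 of 5.

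**Step 3: illustration.** Assume one patient followed for 52 weeks (52 × 7 = 364 days) with one spontaneous bleed, one activity-related bleed and one venipuncture hematoma, all treated with FVIII. The formula in SAP 3.3.2.1 is ABR = bleeds / days × 365.25. One bleed gives 365.25 / 364 = 1.003, two give 2.007 and three give 3.010.

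| Reading | Spontaneous / traumatic / procedural | Treated ABR | Treated spontaneous ABR |
|---|---|---|---|
| *not* deleted | 1 / 1 / 1 | 3.01 | 1.00 |
| Literal: hematoma becomes traumatic | 1 / 2 / 0 | 3.01 | 1.00 |
| Hematoma taken as not a bleed | 1 / 1 / 0 | 2.01 | 1.00 |

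Under the literal reading only the traumatic and procedural counts move. Under the third reading the treated ABR falls by 1.003, and the all-bleeds ABR falls by the same amount. Spread over 70 patients each followed for 364 days, one omitted bleed is 1.003 / 70 = 0.0143 per year, and ten are 0.143.

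**Step 4: the 72-hour wording.** Assumed times, same joint: factor injection at hour 1, oral antifibrinolytic at hour 60, new symptoms and factor injection at hour 100. If only injections or factor count, the gap is 100 − 1 = 99 hours, above 72, and there are two treated bleeds. If any drug counts as treatment, the gap is 100 − 60 = 40 hours and there is one. The difference is again about 0.014 in a 70-patient mean per episode.

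**The case against.** The strongest reply is that the error is harmless in practice. The heading and the second sentence show what was meant. Protocol 4.5.7.3 collects reason, type and location as separate BMQ items, entered by the patient and reviewed by the investigator, and the answer options are not in the documents. *Types of bleeds* in Protocol 6.5.2.1 may mean joint, muscle and other, as in SAP 3.3.2.1.1 and in the joint-bleed definition. Apart from the treated spontaneous ABR, the SAP names no cause table. Protocol 5.3.5.3 partly settles the boundary between adverse events and bleeds: non-serious bleeds consistent with the pre-study disease go only to the BMQ. Nothing is tested.

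Most of this stands, and it makes the point conditional and small. It does not remove the contradiction. The heading of the subsection that defines the causes is itself Definitions of Bleed Types, so a summary by cause is a natural reading of 6.5.2.1.

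Three stronger inferences are not supported:

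- **That the cause summaries are wrong as they stand.** They would be wrong only if the sentence is applied literally and if *type* means cause.
- **That no ABR can change.** This holds for relabelling, but not for the reading that these hematomas are not bleeds.
- **That bleeds treated only with permitted non-factor drugs cannot be separated from untreated ones.** Protocol 3.1 and 4.5.7.3 have the BMQ record the agent or medication and its reason, so they can be. No planned table does so, but the treated and all-bleeds definitions are prespecified, and a further rate for any hemostatic drug would be a preference.

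On the 72-hour rule, the protocol's new-bleed clause runs from injection to injection, and the SAP wording suggests that rates under the rule are an additional presentation. That leaves a wording clarification only.

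**Conclusion.** The procedure/surgery definition contradicts itself. Followed literally, it sends all six of its examples to traumatic, so any summary or listing by cause would overstate traumatic bleeds and understate procedural ones, with none of the five SAP ABRs affected. If a site reads it as *not a bleed*, the all-bleeds count falls, and the treated count falls where factor was given: about 1.00 in the affected patient's 52-week ABR and 0.014 in a 70-patient mean per omitted bleed.

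These sizes assume 364 days of follow-up per patient. The number of procedural bleeds, the BMQ answer options and the way sites would read the sentence are not known from the documents. This is a correction worth making because it is cheap; it does not threaten the primary result.

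**What to change.** - **Protocol 4.5.7.4:** reconcile the two sentences. Deleting *not* is the most natural repair, since it agrees with the heading and the sentence that follows. If the sponsor meant something else, it should say so and state the effect on the counts.
- **SAP 3.3.2.1:** state that bleeds of all causes count in the treated and all-bleeds ABRs. No current text excludes any cause, so this only records what is already implied.
- **SAP bleed summaries:** name the three cause classes separately from joint, muscle and other, so that *type* has one meaning.
- **Minor, SAP 3.3.2.1.1 and Protocol 4.5.7.4:** say which drug classes count as *treatment* in the 72-hour rule, and use one term in both documents.

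The cost is a one-word protocol correction and about three SAP sentences. It needs no new data, no extra tables for other drug classes and no change to the primary definition.
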